4.3 Nonclinical Findings

The results of nonclinical and clinical studies suggest that there are no safety issues with either drug substance, *neltependocel* or Y-27632, of AURN001, and that the minor changes in formulation do not pose a safety risk. The totality of the nonclinical and clinical data with the combination product AURN001 indicate that there are no toxicological reactions (local or systemic) observed in the toxicity studies that would preclude the clinical use of this product.

Additional details about non-clinical findings can be found in the Investigator's Brochure (IB).

4.4 Risk-Benefit Analysis

There is an unmet medical need that warrants intervention for patients in need of corneal transplants.

For patients with visually significant corneal endothelial dysfunction, the only current alternative is watchful waiting in anticipation of a suitable cornea for transplant for either penetrating (PKP) or selective endothelial keratoplasty (DSAEK, DMEK). Watchful waiting may lead to a loss of vision and a burden on the health care of the patient. Disadvantages of PKP include high rates of graft rejection, poor visual quality resulting from irregular astigmatism as well as susceptibility to trauma and suture complications. Disadvantages of EK (DSAEK and DMEK) include surgical complexity, interface haze formation, increased graft detachment rates and high rates of graft failure. While the current available keratoplasty methods are effective, they are complex procedures that require a supply of donor corneas in a 1:1 ratio.

In order to address this medical need, *in vitro* expansion of human CECs is being evaluated as an alternative. This method to prepare human CECs *in vitro*, which can be transferred to the eye, is used to produce AURN001. Additional benefits of this method include smaller surgical incisions that are utilized to deliver treatment without relying on partial or full-thickness donor corneal tissue as carriers for the endothelial cell graft. Thus, in addition to being able to reach a much higher population of patients in need of corneal transplantation, human CEC injection has the

potential to reduce the risk of surgically induced complications, including corneal irregularities and the risk of post-operative graft detachment and/or dislocation of partial or full thickness corneal grafts, while allowing for the potential of one donor cornea to produce cells to treat many patients. The patient experience is improved post-operatively as positioning is limited to the first few hours following surgery, unlike keratoplasty which limits the patients' mobility for several days. In addition, there is a potential lower risk of graft rejection with AURN001 compared with EK or PKP.

In summary, the benefit-risk assessment is such that continued investigation in a clinical study setting is warranted.

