Arm	No. of Subjects	Neltependocel Dose	Y-27632 Dose	Endothelial Polishing?																											
1	20	1.0×10^6	100 μ M	Yes																											
2	20	5.0×10^5	100 μ M	Yes																											
3	20	2.5×10^5	100 μ M	Yes																											
4	20	None	100 μ M	Yes																											
5	20	1.0×10^6	None	Yes																											

	
If the investigator considers it clinically appropriate, after discussion with the medical monitor, subjects who do not meet all study criteria at the Screening Visit may be rescreened within 6 weeks of the Screening Visit. In this case, baseline will be defined by the most recent measure prior to treatment.
 
At the Screening Visit (-77 days to -7 days), subjects who sign the informed consent form (ICF) will undergo screening procedures to determine their eligibility to participate in the study. Surgery will be scheduled in accordance with the manufacturing and delivery schedule of fresh investigational product. The investigators, subjects, and all study site personnel will remain masked to study treatment throughout this process.
 
Only one eye of each subject will receive treatment based on the ocular eligibility criteria; the treated eye will be designated as the “study eye.” If both eyes qualify for treatment, the study eye will be selected at the investigator’s discretion, in consultation with the Medical Monitor, based on the eye where visual acuity is most affected by corneal edema. The other eye will be designated as the “non-study eye.”
 
Although only one eye is being treated, it is important to note that both eyes will undergo all ocular assessments as outlined in the Schedule of Assessments.

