AURN001 is a combination product of allogeneic human corneal endothelial cells (*neltependocel*) and a small molecule drug (Y-27632, a Rho-kinase inhibitor). AURN001's corneal endothelial cells are isolated from transplantation-grade corneas and expanded ex-vivo (Figure 1). The cells harvested for AURN001 express identity marker [REDACTED]

[REDACTED]
They also show the presence of [REDACTED]
[REDACTED]

The presence of Y-27632 in the formulation enhances the cells adhesion by promoting cytoskeletal changes. Furthermore, Y-27632 activates molecular pathways that promote cell survival during delivery to the recipient's cornea, increasing the likelihood of developing a new, fully functional corneal endothelial cell layer. AURN001 is expected to replace and repair the corneal endothelial architecture and restore function, which ultimately reestablishes the fluid balance needed to reinstitute corneal clarity and improve vision¹⁶.

Figure 1 Corneal Endothelial Cell Location and Structure with Expected Y-27632 Mechanism of Action

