4 TRIAL DESIGN

4.1 Description of Trial

This is a multicenter, randomized, double-masked, parallel-arm, dose-ranging, Phase 1/2 study of AURN001 in subjects with corneal edema secondary to corneal endothelial dysfunction. The efficacy and safety of AURN001 will be assessed in a clinical trial setting in North America in adult subjects with corneal edema secondary to corneal endothelial dysfunction. Three doses of AURN001 compared with the 2 components of AURN001 separately (*neltependocel* and Y-27632) will be evaluated to assess the contribution of these 2 elements to the efficacy and safety of AURN001.

This trial will enroll approximately 100 subjects in the 5 treatment arms with approximately 20 subjects per arm. A randomized treatment sequence will be assigned. The sponsor will assess the actual enrollment in each arm on an on-going basis throughout the study to maintain a

randomization ratio of 1:1:1:1:1. The sponsor will make adjustments to the randomized treatment sequence and the number of subjects to be treated in each cohort as needed.

The treatment arms are as follows:

[figure not shown]
Table 1 Treatment Assignment Paradigm

Arm	No. of Subjects	Neltependocel Dose	Y-27632 Dose	Endothelial Polishing?
1	20	1.0×10^6	100 μ M	Yes
2	20	5.0×10^5	100 μ M	Yes
3	20	2.5×10^5	100 μ M	Yes
4	20	None	100 μ M	Yes
5	20	1.0×10^6	None	Yes

This study will have a screening period, a surgery/treatment day during which treatment will be administered, and a 12-month observation period. The primary efficacy analysis will be conducted at Month 6. The study will have up to 10 visits with one optional visit: the Screening Visit (Visit 1, -77 days to -7 days); Surgery/Treatment (Visit 2, Day 1); and Follow-up (Visits 3 through 10, Day 2, Week 1, Week 4, and Months 2 (optional), 3, 4.5, 6, 9, and 12, respectively). Unscheduled visits will be allowed, as deemed necessary by the investigator.

This study will be conducted per the schedule shown in Figure 1.

Figure 1 Study Schematic

Assessments can be found in the Schedule of Assessments in Appendix 1.

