12 TREATMENT EXPOSURE AND NUMBER OF INJECTIONS

12.1 Study Injection Summary

The number of subjects receiving study injections in the Study Eye on Day 1 visit will be summarized with count and percentage by treatment group. Exposure data will be presented in listings.

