13.1.1 Primary Analysis

For the primary endpoint analysis, number and percentage of responders, with associated 2-sided exact (Clopper-Pearson) 95% confidence intervals (CIs), will be presented by treatment group. Proportion of responders will be compared between treatment groups using a two-sided Fisher's exact test. As stated in Section 7.10, subjects who received any rescue surgeries prior to Month 6 or drop out the study due to any reasons prior to Month 6 or missing data at Month 6 will be imputed as treatment failure (i.e. not improve by ≥ 15 letters).

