13.2 Secondary Efficacy Endpoints

Change from baseline in BCVA and CCT at Month 6 will be analyzed using Analysis of covariance (ANCOVA) for the full analysis set. The model will include treatment arm as a categorical variable and baseline as a covariate. Treatment comparison of BCVA and CCT at Month 6 will be conducted. Point estimates, 95% confidence intervals and p-values will be provided. Any data collected at and after rescue visits will not be used. As stated in Section 7.10, LOCF will be used to impute the missing values.

Proportion of subjects having ≥ 10 -letter improvement (2-line gain) from baseline in BCVA at Month 6 will be analyzed using the same method as the analyses of the primary endpoint. For this analysis, missing data will be imputed using the same method as the primary endpoint.

Descriptive summary statistics will be provided for all the secondary endpoints listed in Section 4.2.1.2. Any data collected at and after rescue visits will not be used.

In addition, 3, 2, and 1-line gain and 3, 2, and 1-line loss in BCVA will be summarized by dose and visit. Change from baseline within 10 letters (<10 letters gain and <10 letters loss) will be labeled as 0-line and will also be part of the summary. Summaries will include count, percentage and cumulative percentages. Any data collected at and after rescue visits will not be used.

Change from baseline in BCVA and CCT will also be summarized descriptively using LOCF imputation. Any data collected at and after rescue visits will not be used.

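### Subjects in the four cell arms may share a donor lot and no readable analysis allows for it; how much this narrows the intervals depends on how lots fall across arms, which the documents do not say

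*Protocol*

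**What the plan says.** **The product.** Protocol 4.2 says the cells are "isolated from transplantation-grade corneas and expanded ex-vivo". Protocol 4.4 lists as a benefit of the method "allowing for the potential of one donor cornea to produce cells to treat many patients". The Synopsis adds: "Surgery will be scheduled in accordance with the manufacturing and delivery schedule of fresh investigational product". Protocol Table 1 gives donor cells to Arms 1, 2, 3 and 5; Arm 4 is Y-27632 alone.

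**Allocation.** SAP 4.1 states: "This trial will enroll approximately 100 subjects in the 5 treatment arms with approximately 20 subjects per arm". Protocol 6.1 and 6.3 describe a computer-generated randomised treatment sequence, held at 1:1:1:1:1 by unmasked staff and adjustable by the sponsor. The protocol's revision history for Version 3.0 gives better use of fresh product as the reason for randomising the sequence. No readable text says how lots relate to arms.

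**Analysis.** For the primary endpoint, SAP 13.1.1 gives a Clopper-Pearson interval per arm and adds: "Proportion of responders will be compared between treatment groups using a two-sided" Fisher's exact test. For change in BCVA and CCT, SAP 13.2 specifies an ANCOVA: "The model will include treatment arm as a categorical variable and baseline as a covariate". Protocol 10.7 has a repeated-measures model with arm, time, their interaction and baseline. SAP 14.3 gives Kaplan-Meier medians with 95% intervals. None of these has a donor or lot term.

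**Exposure.** SAP 12.1 is a count: "The number of subjects receiving study injections in the Study Eye on Day 1 visit will be summarized" by treatment group. Donor and lot are not mentioned.

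**The concern.** Subjects injected from one expanded lot share that lot's cell quality. If this affects outcome, their results are positively correlated and an arm of 20 carries less information than 20 independent subjects. Exact binomial intervals, Fisher's test and the ANCOVA all assume independence. The protocol's repeated-measures model deals with correlation within a subject, not between subjects.

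Two things could follow. Per-arm intervals and ANCOVA standard errors could be too small. And if a lot is used in only one arm, a good or poor donor could pass for an effect of that arm. SAP 7.3 says the study is to supply initial estimates for future trial designs, and Protocol 4.5 names the minimally effective dose as an important objective, so both would matter. As the SAP stands, a reader of the report could not tell whether either had happened.

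**Working it through.** **Inputs from the documents:** 20 subjects per arm (5 × 20 = 100, as stated); two-sided alpha 0.05 (SAP 7.4); seven comparisons (SAP 6.2). Those seven are three combination arms against each of two components (3 × 2 = 6), plus component against component (1). Four of them involve Arm 4 (3 + 1); three are between two cell arms (each combination against Arm 5). The plan gives no power, effect size or response rate, so it has no figure to reproduce.

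**Assumed, because the documents are silent:** m subjects per lot (4 or 10), within-lot correlation ICC (0.1 or 0.2), true response rate p (0.5, then 0.3 and 0.7), and no true difference between arms.

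**Step 1. Design effect, lots wholly within an arm.** DE = 1 + (m − 1) × ICC.
- m = 4, ICC 0.1: DE = 1 + 3 × 0.1 = 1.3; effective n = 20/1.3 = 15.4; standard error × √1.3 = 1.14.
- m = 10, ICC 0.1: DE = 1 + 9 × 0.1 = 1.9; effective n = 20/1.9 = 10.5; standard error × √1.9 = 1.38.

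As an illustration, the Clopper-Pearson interval for 10/20 is 27.2% to 72.8%. At the effective n of 10.5 and the same 50%, it is 19.4% to 80.6%.

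**Step 2. Coverage and Fisher size at p = 0.5.** For nested lots, the arm total is a sum of 20/m beta-binomial lots, computed exactly. For lots scattered at random over the 80 subjects in the four cell arms, 200,000 simulated trials were used.

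| Layout | m | ICC | Clopper-Pearson coverage | Fisher size, two cell arms | Fisher size, cell arm v Arm 4 |
|---|---|---|---|---|---|
| Independent | 1 | – | 95.9% | 2.0% | 2.0% |
| Nested in arm | 4 | 0.1 | 92.5% | 4.4% | 3.2% |
| Nested in arm | 4 | 0.2 | 88.9% | 7.2% | 4.5% |
| Nested in arm | 10 | 0.1 | 85.3% | 10.2% | 6.0% |
| Random over cell arms | 4 | 0.1 | 95.1% | 2.1% | 2.3% |
| Random over cell arms | 4 | 0.2 | 94.3% | 2.1% | 2.6% |
| Random over cell arms | 10 | 0.1 | 93.4% | 2.1% | 2.8% |

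If each lot is split evenly between two cell arms, the variance of their difference falls by about 10% (ICC 0.1) to 20% (ICC 0.2), and Fisher size is 1.1% to 1.9%: conservative.

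**Step 3. Other response rates.** At p = 0.3 or 0.7, nested lots with m = 4 and ICC 0.1 give coverage 95.1% and Fisher size 4.9%, both within nominal. With m = 10 and ICC 0.1 they are 89.5% and 10.7%. Random scattering gives coverage of 95.8% to 97.0%.

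**Step 4. ANCOVA, nested lots.** Approximate size = 2 × [1 − Φ(1.96/√DE)].
- Two cell arms: 8.6% at DE 1.3; 15.5% at DE 1.9.
- Cell arm against Arm 4, using the average (DE + 1)/2, that is 1.15 and 1.45: 6.8% and 10.4%.

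The ANCOVA has no built-in conservatism, so it is more exposed than the exact methods.

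**The case against.** The strongest objection is that the harm needs three things the documents do not establish: lots shared by several subjects, a positive within-lot correlation, and lots concentrated within arms. Protocol 4.4 describes a potential of the method, not this trial's supply plan. The product text in Protocol 6.6 is partly blacked out and defers to a handling manual that is not among the documents. A randomised sequence held at 1:1:1:1:1 would tend to scatter lots, and scattered lots do little damage. This stands. It is why the size has to be given for both layouts.

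A reader might infer that the planned intervals are too narrow, or that lots are confounded with arm. The documents support neither as a statement of fact: sharing and nesting can be neither confirmed nor excluded. A reader might also infer that a donor effect would show up as a significant dose difference. SAP 6.2 plans no dose-against-dose test, so for dose the risk lies in informal reading of the arm estimates. The component comparisons are tested, but four of the seven are against Arm 4, where only one side is affected.

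It is also fair to say that inflated test size matters less here. SAP 7.5 and 7.6 call the p-values nominal and set no formal hypothesis, and the exact methods absorb mild clustering. That weakens the error-rate argument but not the one about intervals, because estimation is the study's stated purpose.

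**Conclusion.** The gap is real: no readable analysis allows for correlation between subjects treated from the same donor or lot, and no planned table would show whether it matters. Its size is conditional. With lots largely nested in arms, ICC 0.1 and p = 0.5, nominal 95% intervals cover 92.5% (4 per lot) to 85.3% (10 per lot), and ANCOVA standard errors are too small by a factor of 1.14 to 1.38. With lots scattered at random over the cell arms, the loss of coverage is at most about 1.6 points at p = 0.5 (95% − 93.4%), there is none at p = 0.3 or 0.7, and Fisher's test between cell arms is essentially unaffected. With one subject per lot there is no effect. Arm 4's own interval is unaffected in every case.

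This is therefore a cheap improvement to the SAP, not an error in a stated figure. It bears on the precision and interpretation of estimates for future designs. It does not call for a change to the primary analysis or to the allocation scheme.

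**What to change.** 1. **SAP 12.1:** tabulate the number of donors and lots per arm and the number of subjects per lot. Bring lot identity into the analysis data if it is not there already. Protocol 6.6 requires vial accountability but does not say that donor or lot is captured, so this may need a data transfer.
2. **SAP 13.1.2 (response), where lots serve more than one subject:** add a sensitivity analysis by GEE clustered on lot, with a small-sample variance correction and each Arm 4 subject as its own cluster.
3. **SAP 13.2 (BCVA and CCT), under the same condition:** add the ANCOVA with a random lot effect in the cell arms, again with each Arm 4 subject as its own cluster.
4. **Reporting:** give the number of lots beside the per-arm intervals.

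The cost is one table, one extra model per endpoint and possibly a lot-identity transfer. The sensitivity intervals are likely to be wider, and with few lots the lot effect will be poorly estimated; the report should say so. If the table shows one subject per lot, items 2 and 3 fall away.

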4.4.1 Potential Risks

Potential risks can be categorized as those risks associated with intraocular surgical procedure and those risks associated with the IMP (AURN001).

Potential Risks Associated with Surgery

Potential risks associated with this intraocular procedure include loss of vision, ocular pain and/or discomfort, ocular hyperemia, dry eye, eyelid edema, increased tearing, subconjunctival hemorrhage, corneal or conjunctival abrasion, corneal ulcer, surgical wound leak, shallowing or collapse of the anterior chamber, Descemet's membrane tear, vitreous prolapse, damage to the iris or other structures, changes to the pupil, intraocular bleeding, infection, endophthalmitis, inflammation (uveitis), worsening of corneal edema, posterior capsular opacification (PCO), worsening of cataract, increased IOP, macular edema (including CME and DME), increase in vitreous opacities, posterior vitreous detachment, and retinal detachment, among others.

Potential Risks Associated with the IMP

Potential risks associated with the IMP (AURN001) include ocular pain and/or discomfort, ocular hyperemia, dry eye, failure to improve corneal edema, corneal ulcer, intraocular inflammation (uveitis), infection, endophthalmitis, increased IOP, graft rejection or failure, changes to the pupil, iris or other structures, posterior capsular opacification (PCO), worsening of cataract, increase in vitreous opacities, and macular edema (including CME and DME) among others. Although tumor formation has not been observed in any animal or clinical studies to date, this is a theoretical risk of receiving any cell therapy.

Previous Experience

In prior clinical trials conducted with AURN001 or an earlier formulation in Japan and El Salvador, the most common risks (>5% occurrence) with both the surgical procedure and IMP were as follows:

First In-Human Clinical Trial (Japan)

- Cystoid macular edema (19%)
- Increased IOP (16%)

Other Clinical Trials (Japan)

- Ocular pain (33%)
- Increased IOP (15%)
- Eyelid edema (7%)
- Increased tearing (7%)

Clinical Trials (El Salvador)

- Posterior capsular opacification (PCO) (29%)
- Pupillary disorder (9%)
- Increased IOP (7%)
- Iris disorder (6%)
- Descemet's membrane tear (6%)

Other less common risks (<5% occurrence) included dry eye, blepharitis, macular edema, and anterior chamber inflammation.

4.5 Dose Justification

Human Corneal Endothelial Cells – *Neltependocel*

In humans, the cornea has a diameter of about 11.5 mm and a thickness of 0.5 to 0.6 mm in the center and 0.6 to 0.8 mm at the periphery. Learnings from the current standard of care show that removing the dysfunctional corneal endothelial cells with a graft diameter of approximately 8 mm can improve patient outcomes.

Aurion calculated the number of cells that would be needed to restore [REDACTED] to normal levels [REDACTED]. Given the current procedure involves polishing an area of the corneal endothelium of approximately 8 mm in diameter, to replace those corneal endothelial cells, one would need approximately [REDACTED] to effectively form the monolayer (assuming an equivalent area of polished cornea of approximately 50.27 mm²). In order to account for potential attrition and displacement [REDACTED] of AURN001, approximately [REDACTED] are assumed to be the minimally efficacious dose of *neltependocel*.

Clinical experience from the 3 trials conducted in Japan and the two trials conducted in El Salvador identified 1.0×10^6 *neltependocel* as the most commonly used dose. This dose was found to have a favorable safety profile in conjunction with evidence of biological activity indicated by improvement in vision and reduction in corneal edema (as measured by BCVA and CCT). Lower doses of 5.0×10^5 and 2.0×10^5 were also found to be effective in improving vision and decreasing corneal edema; however, the number of subjects treated at these doses was low.

Three doses of *neltependocel* will be evaluated in this study: (1) 1.0×10^6 with 100 μM of Y-27632, (2) 5.0×10^5 with 100 μM of Y-27632, and (3) 2.5×10^5 with 100 μM of Y-27632. Doses will be delivered by single intracameral injection of a total volume of 300 μL . One of the important objectives of this first US clinical trial is to identify the minimally effective dose of *neltependocel*.

Rho-Kinase Inhibitor – Y-27632

Y-27632 is a novel, low molecular weight, ROCK inhibitor that is injected in conjunction with corneal endothelial cells. Y-27632 enhances the adherence of injected endothelial cells and promotes the development of fully functional corneal endothelial cells. Aurion has conducted human clinical trials in El Salvador where endothelial cells alone were injected intracamerally (n=20) and when compared with the co-injection of endothelial cells with Y-27632, biological activity of the endothelial cells alone was meaningfully diminished as measured by visual acuity improvement, decrease in corneal edema as measured by CCT, overall assessment of corneal clarity, and need for rescue therapy.

In addition, Aurion has performed ROCK activity measurements using an in-vitro biochemical assay and determined that in AURN001's matrix (██████████), a 100 μM concentration of Y-27632 inhibits about 95% of ROCK activity (data on file). Preclinical and clinical studies indicate that this level of ROCK inhibition is sufficient to ensure AURN001 efficacy. ██████████

Furthermore, Aurion's safety pharmacology studies indicate that Y-27632 was well tolerated after intravenous administration of a single dose of up to 100 mg/kg in rabbits (Study 010179.001) as well as in a single dose intravenous and intracameral pharmacokinetic study in rabbits (Study 020179.002). In the doses employed in the rabbit pharmacokinetic study, which are up to 50X the equivalent of the clinical dose, systemic concentrations of Y-27632 fall below the lower limit of quantitation (LLOQ) of the pharmacokinetic assay (10 ng/mL) within 15 minutes after dosing.

Y-27632 has been evaluated in 130 subjects and over 150 procedures in human clinical trials in Japan and El Salvador at doses between 10 μM and 100 μM (single intracameral injection of a total volume of 300 μL). Most of the procedures were conducted using 100 μM dosing in combination with endothelial cells administered by single intracameral injection of a total volume of 300 μL . No systemic pulmonary or cardiovascular toxicity has been observed to date with intracameral administration. The most common adverse events seen are transient IOP elevations and focal iris changes (approximately 5% of subjects). These iris changes are generally considered to be mild and peak around 3 months after injection. As the technique for injecting endothelial cells has improved and refined, the incidence of severity of these iris changes has diminished.

The most recent ongoing clinical study, the Escalon study in El Salvador, is a randomized, double-masked, parallel group, dose ranging study of Y-27632 in 22 subjects which evaluated 10 μM , 20 μM and 100 μM of Y-27632 co-administered with 1.0×10^6 *neltependocel* injected intracamerally in a total volume of 300 μL . This study showed that subjects treated with 20 μM and 100 μM Y-27632 had better evidence of biological activity at six months as measured by

improvements in visual acuity and decreased in corneal edema compared to subjects treated with 10 μM Y-27632 and 1.0×10^6 cells. No differences in safety profile were noted between the three doses of Y-27632. Based on this study, Y-27632 seems to have a wide safety margin with most therapeutic benefit seen between 20 μM and 100 μM . Given these data, this US clinical trial will enroll subjects using 100 μM of Y-27632.

